### 7.2.1. Selection and Timing of Doses

The doses will be administered at approximately the same times on each day. The actual time of all dose administrations will be recorded in the electronic case report form (eCRF).

A cycle is defined as an interval of 28 days (Q2W regimen) and 21 days (Q3W regimen) as shown in [Table JZEA.7](#). A delay of a cycle due to holiday, weekend, bad weather, or other unforeseen circumstances will be permitted for a maximum of 7 days and not counted as a protocol deviation. The reason for the delay should be documented on the eCRF.

The first study treatment will be administered within 7 days after the patient is assigned to a treatment cohort. There should be a minimum of 14 days between doses of study drug for all cohorts in Q2W schedule and 21 days between doses of study drug for the Q3W schedule. However, if there is a delay due to holiday, weekend, bad weather, or other unforeseen circumstances, a flexibility of  $\pm 3$  days is permitted.

A patient may continue to receive LY3434172 until he or she meets one or more of the specified reasons for discontinuation (see Section 8).

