### 7.4. Dose Modification

No dose modification is allowed during the DLT observation period (Cycle 1). See Section 8 for discontinuation criteria. See Section 7.6.1.1 for the definition of DLT-evaluable patients.

After the DLT observation period (Cycle 1), doses of the study drug may be delayed or discontinued to manage specific AEs or other toxicities. Dose reductions are not permitted. All dose modifications should be documented, including the approach taken and a clear rationale for the need for modification.

The investigator must assess whether the toxicity is at least possibly due to study treatment and apply the dose-modification guidelines. Investigators are encouraged to consult Lilly for additional guidance.

If a patient requires a dose delay, study treatment should be resumed within 1 cycle, if possible and appropriate. If study treatment cannot be resumed within 1 cycle, every effort should be made to restart on the first day of the next cycle. In rare circumstances, a delay of >28 days may be permitted before permanent treatment discontinuation, as long as the patient demonstrates clinical benefit, does not have objective progression, and is recovering from the toxicity. Such circumstances must be discussed with the Lilly CRP/CRS.

Adverse events of immune-related etiology are expected because of the study drug's mechanism of action and may occur shortly after the first dose or several months after the last dose. Study treatment must be withheld if the patient experiences a drug-related toxicity or a severe or life-threatening AE. Dose reductions are not permitted.

A 4-hour observation period following the end of LY3434172 administration will occur in Cycles 1 to 3. During observation period, patients treated with LY3434172 should be closely monitored for signs and symptoms indicative of an infusion-related reaction by medical staff from the start of the infusion, in an area where emergency medical resuscitation equipment and other agents (epinephrine, prednisolone, or equivalents, etc.) are available. LY3434172 infusion-related reactions will be defined according to the Common Terminology Criteria for Adverse Events (CTCAE), version 5.0 definition of IRRs.

Table JZEA.9 presents instructions for management of infusion-related reactions associated with LY3434172.

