- b Discontinuation of study treatment is permanent; resumption of study treatment is not allowed. If a toxicity does not resolve to Grade 0-1 or if the corticosteroid dose cannot be reduced to ≤10 mg/day of prednisone or equivalent within 12 weeks, consult with the Lilly CRP about discontinuing study treatment. In cases where corticosteroids are used, they should be appropriately tapered.
- c Immunosuppressive refers to infliximab or cyclophosphamide.

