### 8.1. Discontinuation from Study Treatment

Patients will be discontinued from study treatment in the following circumstances:

- the patient is enrolled in any other clinical study involving an investigational product or any other type of medical research judged not to be scientifically or medically compatible with this study.
- the patient becomes pregnant during the study
- the patient is significantly non-compliant with study procedures and/or treatment as described in Section 7.6
- The patient experiences a DLT (see Section 7.2.2.2) during Cycle 1, a DLT-ET (see Section 7.2.2.2.2), or other unacceptable toxicity
- the patient requires a dose delay of >28 days for Q2W schedule and >21 days for Q3W schedule, except as described in Section 7.4
- the patient, for any reason, requires treatment with another therapeutic agent that has been demonstrated to be effective for treatment of the study indication. Discontinuation from study treatment will occur prior to introduction of the new agent
- the investigator decides that the patient should be discontinued from study treatment, for reasons such as but not limited to confirmed disease progression (see Section 9.1.1).
- the patient requests to be discontinued from study treatment

Patients who are discontinued from study treatment will have follow-up procedures performed as shown in the Schedule of Activities (Section 2).

Discontinuation of study treatment may be considered for patients who meet all of the following criteria:

- have a confirmed complete response (CR), **and**
- have received study treatment for at least 24 weeks, **and**
- have received at least 2 cycles of study treatment beyond the date when the initial CR was declared.

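### In the Q3W cohorts, a dose delay of 22 to 28 days exceeds the Section 8.1 stopping limit but falls short of the Section 7.4 exception, which starts above 28 days for both schedules

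*Protocol*

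**What the plan says.** Section 8.1 of the protocol is a mandatory list, introduced by "Patients will be discontinued from study treatment in the following circumstances". One entry is that "the patient requires a dose delay of >28 days for Q2W schedule and >21 days for Q3W schedule, except as described in Section 7.4". These limits are set separately for the two schedules and equal one cycle in each, since Section 7.2.1 makes a cycle 28 days for Q2W and 21 days for Q3W.

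Section 7.4 asks for treatment to resume within one cycle where possible. Two further sentences follow:

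- Restart sentence: "If study treatment cannot be resumed within 1 cycle, every effort should be made to restart on the first day of the next cycle".
- Exception: "In rare circumstances, a delay of >28 days may be permitted before permanent treatment discontinuation". Three conditions attach to this permission (benefit, no progression, recovery), and the section then adds: "Such circumstances must be discussed with the Lilly CRP/CRS".

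Neither sentence distinguishes Q2W from Q3W. Footnote b of Table JZEA.10 describes what stopping means: "Discontinuation of study treatment is permanent; resumption of study treatment is not allowed".

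**The concern.** Section 8.1 relies on Section 7.4 for its only relief, but the two sections count from different points in the Q3W schedule. The 28-day figure in the exception fits the 28-day cycle and does not carry over to the 21-day one. On the natural reading, a Q3W patient recovering from a toxicity has no stated route to continue after a 25-day delay, but has a conditional route after a 30-day delay. The protocol gives no reason for that ordering.

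The rule decides whether a patient permanently stops treatment, so a misapplication is not reversible under the protocol. Its statistical consequences are descriptive. Dose delays, dose intensity and reasons for discontinuation are summarised (Protocol 10.3.3.1 and 10.3.3.4; SAP 6.7 and 6.12.1), and Protocol 7.2.2.3 includes dose adjustments and chronic intolerance among the data considered for the RP2D. If the handling of a delay depends on which section a site reads, those summaries for A7 and A8 partly reflect that choice.

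**Working it through.** There is no plan figure to reproduce; the check applies the stated day limits to each range of delay.

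**Inputs.** Stopping limit (8.1): over 28 days for Q2W, over 21 days for Q3W. Exception (7.4): over 28 days, both schedules. Cycle length (7.2.1): 28 and 21 days.

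**Step 1. Limits side by side, taking the exception to be the rare-circumstances sentence.** It is the only sentence in 7.4 that speaks of delay before permanent discontinuation.

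| Schedule | Delay | 8.1 limit | 7.4 exception |
|---|---|---|---|
| Q2W | up to 28 days | not exceeded | not needed |
| Q2W | over 28 days | exceeded | available, conditional |
| Q3W | up to 21 days | not exceeded | not needed |
| Q3W | 22 to 28 days | exceeded | not available as written |
| Q3W | over 28 days | exceeded | available, conditional |

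Width of the uncovered range: Q2W 28 − 28 = 0 days; Q3W 28 − 21 = 7 days (22, 23, ..., 28).

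**Step 2. The broader reading of the cross-reference.** Section 8.1 points to 7.4 as a whole, so the restart sentence could also count as an exception. A delay of 22 to 28 days would then not require stopping, and the reversed ordering disappears. The explicit 21-day Q3W limit, however, would then do little in exactly the range where it differs from 28 days. The two readings give different answers for the same patient, and the text does not choose between them.

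**Step 3. Does the restart sentence by itself breach 8.1?** In Q3W, dosing is on Day 1 only (Table JZEA.2). If a Day 1 dose is missed and the cycle calendar is kept, the next Day 1 is 21 days later, and 21 is not greater than 21. With the 3-day visit window it could be 21 + 3 = 24 days. For a missed Day 1 dose in Q2W, the same steps give 28 days, which is not greater than 28, and 28 + 3 = 31 with the window. The sentence therefore passes the limit only if the window is used, cycles are re-anchored or a later cycle is meant, and in that respect the schedules are alike. Only the mismatch in Step 1 is specific to Q3W.

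**Step 4. Can the range be reached?** Section 7.4 asks for a corticosteroid taper of one month after improvement to Grade 1 or less, with no restart until it is complete. Assume a taper of m days beginning on cycle day D, the next Q3W dose planned for day 22, and restart when the taper ends. The delay is D + m − 22. A delay of 22 to 28 days needs D between 44 − m and 50 − m:

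- m = 28: days 16 to 22
- m = 30: days 14 to 20
- m = 31: days 13 to 19

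The range can be reached under the protocol's own instruction. How often it would be cannot be derived from the documents.

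**The case against.** The strongest reply is that Section 8.1 exempts whatever Section 7.4 describes, not one sentence of it, so discontinuation at 22 to 28 days is not strictly required. That is a fair reading and it removes the reversed ordering. It does not remove the conflict, because it leaves the 21-day figure with little effect in the disputed range (Step 2).

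A reader might go further than the documents allow in four ways:

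- That the restart sentence orders sites to breach 8.1 in Q3W. It asks only for every effort, and a restart one cycle later falls exactly on the limit (Step 3).
- That longer delays are simply treated more leniently. Above 28 days, continuation is a rare, conditional permission that requires discussion with the sponsor; the contrast is with no stated permission at all.
- That every Q3W delay is affected. The exception requires recovery from a toxicity, so the ordering problem concerns toxicity delays.
- That two sites would certainly act in opposite ways. Section 7.4 encourages investigators to consult the sponsor, so divergence is possible, not certain.

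It can also be said that response follow-up is largely protected. Table JZEA.3 continues imaging for patients who stop without objective progression, and SAP 6.13.2 includes short-term follow-up assessments in best overall response. That stands.

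**Conclusion.** The inconsistency is real and confined to A7 and A8: seven whole-day values of delay lie above the 8.1 limit and below the start of the 7.4 exception. The Q2W thresholds agree. The ordering problem rests on reading the cross-reference as pointing to the rare-circumstances sentence; on the broader reading, what remains is a 21-day limit with little effect at 22 to 28 days. On either reading a site cannot tell from the text which rule governs.

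The effect is on patient handling and on descriptive exposure and discontinuation data. No sample size or error rate changes, and SAP 6.6 plans no formal hypothesis testing. A reader might put the size at one third of a cohort (1/3 at the minimum of three patients). The documents do not support that as an expected effect: three is a minimum, Protocol 5.2 leaves Q3W size to PK profiles and clinical considerations, and no frequency of such delays is given. Nor do they plan a statistical comparison of Q3W with Q2W; Section 5.1.1 only selects Q3W doses for similar exposure.

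**What to change.** Reconcile Sections 7.4 and 8.1 for the 21-day cycle in two respects:

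- Make the delay at which the 7.4 exception begins correspond to the schedule-specific limit in 8.1, so that no range of delay is left without a stated rule.
- State whether the sentence on restarting at the first day of the next cycle falls within the 8.1 exception.

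The limit itself, and whether any delay beyond it is acceptable, is for the sponsor's clinical team to set. The cost is about one clause in 7.4 or 8.1, plus a short clarification of the cross-reference. The statistical plan needs no change.

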### ***8.1.1. Discontinuation of Inadvertently Enrolled Patients***

If Lilly or the investigator site identifies a patient who did not meet enrollment criteria and who was inadvertently enrolled, a discussion must occur between Lilly CRP/CRS and the investigator to determine if the patient may continue in the study. If both agree that it is medically appropriate to continue, the investigator must obtain documented approval from Lilly CRP/CRS to allow the inadvertently enrolled patient to continue in the study with or without study treatment. Safety follow-up is as outlined in the Schedule of Activities (Section 2).

## **8.2. Discontinuation from the Study**

Patients will be discontinued from the study in the following circumstances:

- participation in the study needs to be stopped for medical, safety, regulatory, or other reasons consistent with applicable laws, regulations, and good clinical practice (GCP).
- the patient becomes pregnant during the study. See Section 9.1.1.3 regarding regulatory reporting requirements on fetal outcome and breast-feeding
- the investigator decides that the patient should be discontinued from the study
- the patient requests to be discontinued from the study
- the patient's legal representative requests that the patient be discontinued from the study

Patients who discontinue from the study early will have end-of-study procedures performed as shown in the Schedule of Activities (Section 2).

## **8.3. Lost to Follow-Up**

A patient would be considered lost to follow-up if he or she repeatedly fails to return for scheduled visits and is unable to be contacted by the study site. Study site personnel are expected to make diligent attempts to contact patients who fail to return for a scheduled visit or who the site is otherwise unable to follow-up.

## 9. Study Assessments and Procedures

Section 2 provides the Schedule of Activities for this study.

Appendix 2 provides a list of the laboratory tests that will be performed for this study.

Appendix 4 provides the schedule for collection of samples in this study.

Unless otherwise stated in the following subsections, all samples collected for specified laboratory tests will be destroyed within 60 days of receipt of confirmed test results. Certain samples may be retained for a longer period, if necessary, to comply with applicable laws, regulations, or laboratory certification standards.

### 9.1. Efficacy Assessments

Tumor assessments will be performed for each patient at the times shown in the Schedule of Activities (Section 2). A secondary objective of the study is to document efficacy.

RECIST 1.1 (Eisenhauer et al. 2009) will be applied as the primary criteria for assessment of tumor response and disease progression. Local tumor imaging (investigator assessment with site radiological reading) will be used.

Computed tomography (CT) is the preferred imaging method for the majority of patients. Magnetic resonance imaging should only be used when CT is contraindicated or for imaging in the brain. The same imaging technique should be used for a patient throughout the trial. Imaging should include the chest, abdomen, and pelvis. Intravenous and oral contrast is required unless medically contraindicated.

#### At Study Baseline:

- Must be performed within 28 days prior to the first dose of study drug.
- Scans performed as part of routine clinical management are acceptable for use as initial tumor imaging if they are of diagnostic quality and performed within protocol-required time frame as described above.

#### During Study Treatment:

- Performed every 8 weeks ( $\pm 7$  days) for the 28-day cycle cohorts and every 6 weeks ( $\pm 7$  days) for the 21-day cycle cohorts, by the investigator, with confirmatory assessment obtained at the next routine scheduled imaging time point (See Section 9.1.1).
- Per RECIST v1.1, partial response (PR) or complete response (CR) should be confirmed by a repeat tumor imaging assessment, preferably at the next scheduled imaging visit, and not less than 4 weeks from the date the response was first documented. Thus, for Study JZEA, tumor imaging for confirmation of response may be performed at the earliest four weeks after the first indication of response, or at the next scheduled scan, whichever is clinically indicated.
- Continue to perform imaging until whichever of the following occurs **first**:
  - disease progression confirmed by the second radiographic examination

- the start of new anticancer treatment
- withdrawal of consent
- death
- study completion

If radiologic imaging verifies an initial assessment of progressive disease (PD), apply RECIST 1.1 with confirmatory scan for disease progression (Section [9.1.1](#)).

**During the Poststudy Treatment Period:** Tumor assessments may continue for patients who are withdrawn from the study treatment for reasons other than disease progression every 8 to 12 weeks depending on standard-of-care.

See Section [10.3.2](#) for definitions of the efficacy endpoints.

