### ***9.1.1. RECIST 1.1 with Confirmatory Scan for Disease Progression***

#### **9.1.1.1. Rationale for RECIST 1.1 with Confirmatory Scan for Disease Progression**

Response to immunotherapy may differ from responses typically observed with cytotoxic chemotherapy, including the following (Wolchok et al. 2009; Nishino et al. 2013):

- Response to immunotherapy may be delayed.
- Response to immunotherapy may occur after PD by conventional criteria.
- The appearance of new lesions may not represent PD with immunotherapy.
- Stable disease while on immunotherapy may be durable and represent clinical benefit.

Therefore, to adequately characterize additional patterns of response and progression specific to patients treated with immunotherapy, which cannot be captured by conventional criteria such as RECIST 1.1, alternative measures of tumor assessment have been developed, such as RECIST 1.1 with confirmatory scan for disease progression. Clinically stable patients may continue treatment until disease progression (per standard RECIST 1.1) is confirmed. See [Table JZEA.11](#) for further details and timing of confirmatory scans for PD.

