**Table JZEA.11. Summary of Response Assessment by RECIST, RECIST with Confirmatory Scan for PD, and irRC**

Definition	Used in Study JZEA		Not Used in Study JZEA
	RECIST v1.1	RECIST 1.1 with Confirmatory Scan for PD	irRC (Wolchock et al. 2009), irRECIST (Nishino et al. 2013) iRECIST (Seymour et al. 2017)
New lesion	The presence of new lesion defines progression	The presence of new lesion defines progression	The presence of new lesion does not define progression. The measurements of the new lesion(s) are included in the sum of the measurements.
Confirmation of PD	Not required	PD, in the absence of clinically significant deterioration, requires confirmation with repeat imaging after 4 to 6 weeks. After initial PD following RECIST v1.1, shift to “RECIST 1.1 with confirmatory scan for PD”.	Required

Abbreviations: irRC = immune-related response criteria; irRECIST = immune-related Response Evaluation Criteria in Solid Tumors; PD = progressive disease; RECIST = Response Evaluation Criteria in Solid Tumors.

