#### **9.1.1.2. Application of RECIST 1.1 with Confirmatory Scan for Disease Progression**

For Study JZEA, based on the unique response to immunotherapy and guidelines from regulatory agencies (for example, the EMA guideline on the evaluation of anticancer medicinal products in man for immune-modulating anticancer compounds [EMA 2013]), the following will be applied, in addition to standard RECIST 1.1 criteria:

- If radiologic imaging verifies initial PD, tumor assessment should be repeated 4 to 6 weeks later in order to confirm PD in the absence of clinically significant deterioration. Study treatment will continue between the initial assessment of progression and confirmation for progression.

“Clinically significant deterioration” is considered to be rapid tumor progression that necessitates treatment with anticancer therapy other than study treatment, or symptomatic progression that requires urgent medical intervention (for example, central nervous system metastasis, respiratory failure due to tumor compression, or spinal cord compression).

- In the case of clinically significant deterioration, the patient will be discontinued from study treatment (Section 8.1).
- Patients who continue to receive clinical benefit and who do not have clinically significant deterioration despite evidence of objective PD by the confirmatory scan may continue study treatment at the discretion of the investigator, in consultation with the Lilly CRP/CRS.

In determining whether or not progression can be confirmed, the site study team should consider all target lesions, nontarget lesions, and new lesions, and assess according to RECIST 1.1.

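### Protocol Section 9.1 times the confirmatory scan for progression at the next routine scan (nominally 8 weeks in Q2W cohorts), against 4 to 6 weeks in Table JZEA.11 and Section 9.1.1.2

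*Protocol*

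**What the plan says.** Protocol Section 9.1, During Study Treatment, first bullet: imaging is every 8 weeks in the 28-day-cycle cohorts and every 6 weeks in the 21-day-cycle cohorts, each with a window of 7 days either way, "with confirmatory assessment obtained at the next routine scheduled imaging time point". The bullet refers to Section 9.1.1. The second bullet deals separately with confirmation of complete or partial response. Imaging ends, among other reasons, at "disease progression confirmed by the second radiographic examination". The subsection then says: "If radiologic imaging verifies an initial assessment of progressive disease (PD), apply RECIST 1.1 with confirmatory scan for disease progression".

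Section 9.1.1 concerns progression only. Section 9.1.1.1 sends the reader to Table JZEA.11 "for further details and timing of confirmatory scans for PD". That table says that PD without clinically significant deterioration "requires confirmation with repeat imaging after 4 to 6 weeks". Section 9.1.1.2 says that "tumor assessment should be repeated 4 to 6 weeks later in order to confirm PD", and adds: "Study treatment will continue between the initial assessment of progression and confirmation for progression".

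Table JZEA.1 (Q2W cohorts) lengthens the routine imaging interval to about 12 weeks for patients still on treatment after one year.

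**The concern.** One scan has two timing rules. The bullet does not name PD, but it cites the section on confirming progression, and response confirmation has its own bullet, so PD is the natural reading. In the Q2W cohorts the two rules are incompatible at their nominal times, and no text such as a whichever-is-earlier clause or a call for an unscheduled scan settles which prevails.

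The confirmatory scan marks the end of a period in which a patient with radiographic progression keeps receiving a first-in-human agent under an addendum consent (Section 9.1.1.3). A late scan lengthens that period. It can also affect the analysis: SAP Section 6.13.6 takes best response over the assessments before PD together with the confirmation stage, so sites working to different rules would contribute stages of different length to irORR and irDCR.

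**Working it through.** The plan gives no figure of its own to reproduce; the check is scheduling arithmetic.

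**Inputs**
- Confirmation window: 4 to 6 weeks = 28 to 42 days (Table JZEA.11, Section 9.1.1.2).
- Routine interval: 56 days (Q2W) or 42 days (Q3W), ±7 days (Section 9.1); about 84 days for Q2W after year 1 (Table JZEA.1).
- Q2W dosing on days 1, 15, 29 and so on (Table JZEA.1).

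**Interval from PD scan to next routine scan.** Let *a* and *b* be the deviations in days of the PD scan and the next scan, each an integer from −7 to 7. The interval is *L* + *b* − *a*, where *L* is the routine interval. There are 15 × 15 = 225 pairs.

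| | Q2W, *L* = 56 | Q3W, *L* = 42 |
|---|---|---|
| Nominal interval | 56 d; 56 − 42 = 14 d late | 42 d; complies |
| PD scan on nominal day (*a* = 0) | 49–63 d; 0 of 15 days comply | 35–49 d; 8 of 15 comply |
| Both windows used | 42–70 d; 1 of 225 pairs complies | 28–56 d; 120 of 225 comply |

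The one compliant Q2W pair is *a* = +7, *b* = −7. Over all Q2W pairs the excess past 42 days runs from 0 to 28 days, with mean 56 − 42 = 14 days. For Q3W, compliance needs *b* ≤ *a*, which gives (225 + 15)/2 = 120 pairs. After year 1 in Q2W the excess is about 84 − 42 = 42 days, or 6 weeks.

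**Doses between the PD scan and confirmation (Q2W).** Take PD at the nominal week-8 scan (day 57), and assume that a scan precedes a dose due the same day.
- Confirmed at 4 weeks (day 85): doses on days 57, 71 = 2.
- At 6 weeks (day 99): days 57, 71, 85 = 3.
- At 8 weeks (day 113): days 57, 71, 85, 99 = 4.
- At 12 weeks: 6 doses, using the same day pattern.

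Against a 6-week scan, the bullet therefore adds 4 − 3 = 1 dose, and about 6 − 3 = 3 doses after year 1.

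With the scan windows, the extra doses are those falling from day 99 + *a* up to, but not including, day 113 + *b*. The day-99 dose counts when *a* ≤ 0 (8 values) and the day-113 dose when *b* > 0 (7 values). Hence:
- no extra dose in 7 × 8 = 56 pairs;
- one in 8 × 8 + 7 × 7 = 113 pairs;
- two in 8 × 7 = 56 pairs.

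The mean is 1.

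**The case against.** The strongest reply is that the documents already resolve the matter. The bullet cites Section 9.1.1, the end of the same subsection and Table JZEA.1 send initial PD there too, and Section 9.1.1.1 names Table JZEA.11 for the timing. A site that follows the references arrives at 4 to 6 weeks. This settles which rule is intended, but it does not remove the other one: the bullet states an operative timing that a Q2W site cannot follow and still comply with Section 9.1.1.2, except at exactly 6 weeks.

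A second reply is that the bullet could concern response confirmation, for which the next scheduled visit is the preferred time. That is possible on the wording, but the reference to Section 9.1.1 and the separate response bullet weigh against it.

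Third, the consequences are small. This largely stands:
- Section 9.1.1.2 uses advisory wording, although Table JZEA.11 is firmer, and no text disqualifies a later scan. On the natural reading of SAP Section 6.13.6, confirmed irPD keeps the initial PD date.
- Only clinically stable patients who meet Section 9.1.1.3 are treated in this period.
- Confirmation need not end treatment: a clinically stable patient who is still benefiting "despite evidence of objective PD by the confirmatory scan may continue study treatment at the discretion of the investigator". The sponsor must be consulted.

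Finally, the day-pair counts add detail rather than force. The point rests on the nominal 8 weeks against 4 to 6.

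**Conclusion.** The inconsistency is real and should be corrected. In year 1 a Q2W site that follows the bullet confirms PD nominally 2 weeks late (0 to 4 weeks with both scan windows), at a cost of about one extra dose (0 to 2). After year 1 it is about 6 weeks late and three extra doses, for the patients still on drug. In year 1 the nominal Q3W scan meets the window. Appendix 10 shows the same 12-week sentence for the Q3W cohorts; if it applies, their excess after year 1 would also be about 6 weeks.

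The dose counts concern only patients who would stop at confirmed PD. They assume on-schedule dosing (the ±3-day cycle window is ignored), and the means weight every permitted scan day equally. The effect is confined to dosing after progression and to the descriptive immune-related endpoints. The primary objective and the standard RECIST 1.1 progression date are untouched.

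**What to change.** In the first During Study Treatment bullet of Protocol Section 9.1, replace the clause on the next routine scan with a statement that PD is confirmed by repeat imaging 4 to 6 weeks after initial PD, matching Table JZEA.11 and Section 9.1.1.2. Leave response confirmation in its own bullet.

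The cost is one protocol clause. Q2W patients with initial PD need one off-cycle scan, which Section 9.1.1.2 already calls for. In the Q3W cohorts during year 1, a routine scan on its nominal day already satisfies the rule; one that would fall more than 6 weeks after the PD scan needs to be brought forward. No SAP change is required.
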